6.2. Adjustments for Covariates

Stratification factors of this study include region (US, OUS), historical use of SmartGuard/Threshold Suspend (Yes, No) and HbA1c stratum ($\leq 7.3\%$, $> 7.3\%$). Stratification factors will be entered into the IWRS for randomization and also collected in the database by eCRF or central laboratory. The analysis models will use the stratification factors as collected in the database.

Other analyses will include the stratification factors as noted in Sections 6.11 to 6.14.

6.3. Handling of Dropouts or Missing Data

For continuous variables, missing data will be addressed by using a MMRM analysis for continuous longitudinal variables. The MMRM model provides consistent estimator when data is missing at random. The model implicitly adjusts for missing data through a variance-covariance structure.

Otherwise, handling of dropouts or missing data is described for each individual primary or secondary endpoint in Sections 6.11 to 6.13.

6.4. Multicenter Studies

This study is conducted at multiple investigators sites in U.S and Spain. All analyses using region in the model will use region (US, OUS), unless otherwise specified.

6.5. Multiple Comparisons/Multiplicity

Treatment group comparisons will be performed for the primary objective (Section 6.11.1) at the full significance level of 0.05. No multiplicity adjustments will be made for secondary and exploratory objectives.

6.6. Patient Disposition

Patient disposition will be displayed in a flowchart showing the number of patients entered, enrolled, randomized, and discontinued across all study periods.

Frequency counts and percentages of all randomized patients completing and discontinuing from the study will be presented for overall and by each treatment sequence and period. Reasons for discontinuation from the study will be summarized for overall and by treatment sequence and period. Reasons for discontinuation from the study at Visit 801 will be summarized by the randomized treatment sequences.

Frequency counts and percentages of all patients entered, enrolled, and discontinued from the study during the lead-in period will be summarized. Reasons for discontinuation during screening will be summarized for the Entered Population. Reasons for discontinuation from the study during the lead-in period will be summarized for the Enrolled Population.

A listing of the primary reason for study discontinuation will be generated for the Enrolled Population.

Patient allocation by investigator, grouped by country, will be summarized indicating the number of patients who enter the study, the number of patients who participate in the lead-in period, the number of patients who are randomized to treatment sequences and the number of patients who discontinue the study.

A listing will be generated for the Randomized Population, including the following variables but not limited to: investigator ID, patient ID, date of signature of informed consent form, randomization treatment sequence assignment, randomization date, first and last dose date in each treatment period (lead-in, Period I and Period II).

6.7. Patient Characteristics

A summary table for overall and by treatment sequence will be generated for patient characteristics at study entry using all randomized patients. The following variables will be included but not limited to: age, age groups (<40 and \geq 40 years, and <65, \geq 65 to <75, \geq 75 to <85, \geq 85 years), sex, country, region, ethnicity, race, height, weight, body mass index (BMI), BMI groups (<25, \geq 25 to <30, \geq 30 to <35, and \geq 35 kg/m²). No statistical comparisons between treatment sequences will be performed. For continuous variables, the following statistics will be provided: mean, SD, minimum, maximum, and median. For categorical variables, summary statistics will include sample size, frequency and percentage. A listing of patient characteristics at baseline will be provided.

A similar summary of diabetes characteristics will also be generated. The following variables will be included but not limited to: duration of diabetes, duration of CSII use, pump model, the type of rapid-insulin at study entry, total daily dose at study entry, historical use of SmartGuard/Threshold Suspend at study entry, HbA1c at study entry and baseline, HbA1c stratum at baseline.

A listing of patients whose stratification factor value entered into the IWRS (for treatment group assignment) is different from the clinical database will also be provided.

The total daily insulin dose for the last 3 days prior to screening will be entered into the eCRF. The dose at study entry will be calculated as the mean of the doses for the last 3 days prior to the visit. Doses will be summarized in U and U/kg. Total daily insulin dose will also be presented by the definitions in protocol exclusion criterion #28 (\leq 1.2 U/kg, $>$ 1.2 U/kg).

For all randomized patients, the number and percentage of patients with historical conditions will be summarized using Medical Dictionary for Regulatory Activities (MedDRA) Preferred Term (PT) (without regard to System Organ Class (SOC)), and the number and percentage of patients with preexisting conditions will also be summarized using MedDRA PT (without regard to SOC). Historical conditions are conditions that end prior to informed consent and preexisting conditions are conditions that are still ongoing at informed consent. Events will be ordered by decreasing frequency.

All baseline measures will be summarized for overall and by treatment sequence. No statistical comparison between treatment sequences will be performed given the small sample size of this study.

6.8. Treatment Compliance

No analysis for treatment compliance is planned for this study.

6.9. Important Protocol Deviations

Important protocol deviations that potentially compromise data integrity or patients' safety will be summarized by treatment group for all randomized patients. [Table ITSI.6.3](#) lists the categories/subcategories of important protocol deviations, source of identification, and the method to identify each deviation.

Table ITSI.6.3. Description of Important Protocol Deviations

Category	Sub-categories	Trial Specific	Source	Methods of Identification
Informed Consent	Informed Consent Not Obtained	N/A	Mixed (monitoring and clinical database)	Compare all assessment dates to ICD date (except those assessments that may occur before ICD, e.g., disease assessments).
Informed Consent	Improper Consent	N/A	Mixed (monitoring and clinical database)	Failure to re-consent after an ICD amendment at first possible visit. Unauthorized personnel administered ICD. Patient signed incorrect version of ICD. ICD was not dated. ICD was lost.
Informed Consent	Revoke Consent	N/A	Mixed (Monitoring and clinical database)	Patient revoked ICD. If patient revokes consent, data are excluded from the study.
Eligibility	Inclusion/Exclusion	Type of Patient and Disease Characteristics	Mixed (monitoring and clinical database)	CRF (Medical History: Diabetes Duration panel) data indicate diagnosis date of T1D <1 year prior to screening date (#1). CRF (Prior Diabetes Therapies/Concomitant panel) data to indicate start date for continuously using insulin < 1 year prior to screening date (#1). Also identified by CRA as captured in sCTMS.

Category	Sub-categories	Trial Specific	Source	Methods of Identification
Eligibility	Inclusion/Exclusion	Age not in compliance with entry criteria	Mixed (monitoring and clinical database)	CRF data indicate the age <18 yrs at Visit 1 (#2). Also identified by CRA as captured in sCTMS.
Eligibility	Inclusion/Exclusion	Previous non-insulin antihyperglycemic medications	Mixed (monitoring and clinical database)	CRF Prior Diabetes Therapies / Concomitant Therapy panel data to indicate not compliant with entry criteria #42. Also identified by CRA as captured in sCTMS.
Eligibility	Inclusion/Exclusion	Previous insulin therapy	Mixed (monitoring and clinical database)	CRF Prior Diabetes Therapies / Concomitant Therapy panel data to indicate not compliant with entry criteria #5 [basal insulin was used for >14 consecutive days during the 6 months prior to screening], #6, or #41 Also identified by CRA as captured in sCTMS.
Eligibility	Inclusion/Exclusion	Other Inadvertent Enrollment	Non Programmable (monitoring)	Identified by CRA as captured in sCTMS.
Eligibility	Inclusion/Exclusion	Use of non-study device or materials	Non Programmable (monitoring)	Use of non-study pumps, infusion sets, and use of Enlite sensor (enables Smart-Guard)
Investigational Product	Treatment Assignment/ Randomization Error	N/A	Non Programmable (monitoring)	IWRS data entry errors that impact patient stratification, for example, lab data indicated different strata from IWRS stratification report. Dispensing error: Patient is assigned to a treatment, but site gave a different treatment to the patient.
Investigational Product	Unblinding	N/A	Non Programmable (monitoring)	Any inadvertent unblinding affecting, patients, investigator or sponsor.
Investigational Product	Patient Took Medication Not Fit for Use	N/A	Non Programmable (monitoring)	Study Drug not fit for use administered to patient.

Category	Sub-categories	Trial Specific	Source	Methods of Identification
Investigational Product	Other	Use of expired CT material	Non Programmable (monitoring)	Also identified by CRA as captured in sCTMS.
Study Procedures	Other	Infusion set change frequency	Programmable (clinical database)	eCOA data indicate that $\geq 75\%$ of routine infusion set changes are not in the range of 72 ± 4 hours during the two 6-week treatment periods (#13).
Study Procedures	Violation of Discontinuation Criteria	N/A	Mixed (monitoring and clinical database)	Patients not discontinued from study despite having met protocol specified discontinuation criteria. Also identified by CRA as captured in sCTMS. Protocol Section 8 (e.g., patient(s) become pregnant according to central/local lab or CRF AE page).
Study Procedures	Excluded Conmeds	N/A	Mixed (monitoring and clinical database)	CRF Prior Diabetes Therapies / Concomitant Therapy panel data to indicate not compliant with entry criteria #43 and study-specific restriction on concomitant therapies Table ITSI.5 in the study protocol. Also identified by CRA as captured in sCTMS.
Study Procedures	Visit Schedule Criteria	N/A	Programmable (clinical database)	CRF data indicate that two consecutive office visits are completely missing.
Study Procedures	Other	Electronic Clinical Outcomes Assessment (eCOA)	Mixed (monitoring and clinical database)	Patients did not use eCOA system during the entire study. Comparison of patient data from CRF and eCOA to identify randomized patients who have no eCOA data entered.
Administrative/ Oversight	Suspected Misconduct	N/A	Non Programmable (monitoring)	Site staff sharing account details for systems (e.g., IWRS, EDC, eConsent or ePresentOnline). Suspected falsification of data.

Category	Sub-categories	Trial Specific	Source	Methods of Identification
Administrative/ Oversight	PI oversight	N/A	Non Programmable (monitoring)	Identified by CRA as captured in sCTMS.
Safety	Safety Mailings	N/A	Non Programmable (monitoring)	Lack of, significant delay in safety mailing review (significant delay defined as a delay of 1 month).
Safety	SAEs	Failure to report SAE in 24 hours	Non Programmable (monitoring)	Failure to report an SAE within 24 hours of the investigator being made aware of the SAE. Failure to respond to SAE queries.
Safety	Other	Failure to report product complaint within 24 hours	Non Programmable (monitoring)	Identified by CRA as captured in sCTMS.

Abbreviations: CRA = clinical research associate; CRF = clinical (case) report form; CT = clinical trial; ICD = informed consent document; EDC = Electronic Data Capture; ITSI = Study I8B-MC-ITSI; IWRS = interactive Web Response System; OAM = oral antihyperglycemic medication; MedDRA = Medical Dictionary for Regulatory Activities; NA = not applicable; SAE = serious adverse event; sCTMS = Simplicity Clinical Trial Management System; T1D = type 1 diabetes; yrs = years.

#: number of inclusion/exclusion criteria in the protocol.

The listing of important protocol deviations for all randomized patients during the entire study, will be provided in the CSR.

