### 8.2. Discontinuation from the Study

Patients will be discontinued in the following circumstances:

- The investigator may decide that the patient should stop IP. If this decision is made because of an AE, SAE, or a clinically significant laboratory value, the study drug is discontinued for that patient and appropriate measures are to be taken. Lilly or its designee is to be alerted immediately
- The patient may decide to stop IP
- The patient becomes pregnant
- If an investigator, study site personnel performing assessments, or patient is unblinded, the patient must discontinue IP
- Frequent use of prohibited concomitant medication
- Use of pump that is not allowed
- Defiant continued use of SmartGuard/Threshold Suspend technology
- The patient has not used IP for more than 7 consecutive days
- Enrollment in any other clinical study involving an IP or enrollment in any other type of medical research judged not to be scientifically or medically compatible with this study
- Participation in the study needs to be stopped for medical, safety, regulatory, or other reasons consistent with applicable laws, regulations, and good clinical practice (GCP)
- Investigator decision

- the investigator decides that the patient should be discontinued from the study
- if the patient, for any reason, requires treatment with another therapeutic agent that has been demonstrated to be effective for treatment of the study indication, discontinuation from the study occurs prior to introduction of the new agent
- Subject decision
  - the patient requests to be withdrawn from the study
- **Discontinuation due to a hepatic event or liver test abnormality:** patients who are discontinued due to a hepatic event or liver test abnormality should have additional hepatic safety data collected via electronic case report form (eCRF).

Discontinuation for abnormal liver tests **should be** considered by the investigator when a patient meets one of the following conditions after consultation with the Lilly designated medical monitor:

- ALT or AST >8X ULN
- ALT or AST >5X ULN for more than 2 weeks
- ALT or AST >3X ULN and TBL >2X ULN or international normalized ratio >1.5
- ALT or AST >3X ULN with the appearance of fatigue, nausea, vomiting, right upper-quadrant pain or tenderness, fever, rash, and/or eosinophilia (>5%)
- alkaline phosphatase (ALP) >3X ULN
- ALP >2.5X ULN and TBL >2X ULN

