- ALP >2.5X ULN with the appearance of fatigue, nausea, vomiting, right quadrant pain or tenderness, fever, rash, and/or eosinophilia (>5%)

Patients discontinuing from the study prematurely for any reason should complete AE and other safety follow-up per Section 2 (Schedule of Activities), Section 9.2 (Adverse Events), and Section 9.4 (Safety) of this protocol, with the exception of those who discontinue during the lead-in period will not need to have laboratory tests drawn.

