6.1. General Considerations

Statistical analysis of this study will be the responsibility of Eli Lilly and Company (hereafter Lilly). Any change to the data analysis methods described in the protocol will require an amendment ONLY if it changes a principal feature of the protocol. Any other change to the data analysis methods described in the protocol, and the justification for making the change, will be described in this SAP and/or in the clinical study report (CSR). Additional exploratory analyses will be conducted, as deemed appropriate.

For purposes of analysis, the following populations are defined in [Table ITSI.6.1](#):

Table ITSI.6.1. Patient Populations

Population	Description
Entered	All patients who give informed consent.
Enrolled	All patients who receive at least 1 dose of open-label insulin lispro in the 2-week lead-in period.
Randomized	All patients who are randomly assigned to study treatment at Visit 3. Treatment group will be defined on the basis of the treatment the patients are assigned to.
Safety	All randomized patients who receive at least 1 dose of the randomly assigned IP. Treatment group will be defined on the basis of the treatment the patients are assigned to.
CGM Population	All randomized patients who receive at least 1 dose of the randomly assigned IP, and have CGM data from at least 1 collection period (lead-in, Period I and Period II). Treatment group will be defined on the basis of the treatment the patients are assigned to.

Safety analyses will be conducted on the Safety Population. Analyses of adverse events (AEs) will include all data collected during the course of the entire 6-week treatment period for each treatment group regardless of IP use. Analyses of hypoglycemia will be conducted on data collected prior to permanent discontinuation (i.e., last dose) of IP in each 6-week treatment period. Unless otherwise specified, pump-related safety analyses (e.g., infusion set failures, interstitial glucose reduction rate) will exclude data (if any) that are collected while patients temporarily are off pump or off IP. Data collected during the safety follow-up period will not be used for comparisons between treatment groups.

Unless otherwise specified, exploratory efficacy analyses will be conducted on the Randomized Population. CGM outcome analyses will be conducted on the CGM Population.

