Unless otherwise noted, all tests of treatment effects will be conducted at a 2-sided alpha level of 0.05, and confidence intervals (CIs) will be calculated at 95%, 2-sided. If conducted, all tests of interactions between treatment groups and other factors will be conducted at a 2-sided alpha level of 0.10.

The definitions of baseline and post-baseline for the safety and efficacy analyses depend on which analysis period is being used. The following analysis periods will be used:

- Lead-in Period – Visits 2-3
- 12-Week Treatment Period while on IP – from first dose to last dose of IP in each 6-week randomized treatment period (Period I and Period II)
- 12-Week Treatment Period Regardless of IP use – from randomization to Week 6 of each randomized treatment period (including all data regardless of IP use)
- Safety Follow-up Period – Visit 801

Table ITSI.6.2 describes the rules for determining the patient population, baseline and postbaseline observations for the different analysis periods. The data in the lead-in and the safety follow-up visit, if summarized, will be for overall, not by treatment group.

The data on IP is defined based on the following rules:

- for data only measured at an office visit (for example, HbA1c), if the office visit date (or laboratory sample collection date) is within 14 days of the date of last study drug dose of the randomized treatment period (Period I or Period II), then postbaseline data measured at or prior to that office visit will be considered as data on IP.
- for data collected as running records with an exact date and/or time stamp such as diary entries where the date and time of the measures was not tied with the date of an office visit, postbaseline data with date and time \leq (last study drug dose date and time) will be considered as data on IP.

For continuous measures, summary statistics will include sample size, mean, standard deviation (SD), median, minimum, and maximum for both the actual and the change from baseline measurements. Least squares (LS) means and standard errors derived from the analysis models will also be displayed for the change from baseline measurements. Treatment comparisons will be displayed showing the treatment difference LS means and the 95% CIs for the treatment differences, along with the p-values for the treatment comparisons.

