6.11. Safety Analyses

6.11.1. Primary Outcome and Methodology

The primary objective of this study is to compare LY900014 and insulin lispro with respect to the rate (events/patient/30 days) of infusion set failures that lead to premature infusion set changes, due to a pump occlusion alarm OR due to unexplained hyperglycemia with blood glucose (SMBG) >250 mg/dL (13.9 mmol/L) that does not decrease within 1 hour following a correction bolus delivered via the pump, during the 6-week treatment period.

To be considered as the primary endpoint, an infusion set failure must result in a premature infusion set change due to:

1. pump occlusion alarm(s), OR
2. unexplained hyperglycemia that meets the following conditions:
 - Associated with a non-meal-related correction bolus delivered via the pump at least 1 hour before the infusion set change
 - Most recent self-monitored blood glucose (SMBG) within 1 hour before the correction bolus >250 mg/dL (13.9 mmol/L)
 - At least 1 SMBG obtained following the correction bolus prior to the infusion set change
 - Within 1 hour (+10 minutes) following the correction bolus, the most recent SMBG prior to the infusion set change does not indicate a decrease in blood glucose

If more than 1 non-meal-related correction bolus is given for an unexplained hyperglycemia, only the first correction bolus time will be used to determine the 1 hour (+10 minutes) timeframe following the correction bolus as described in Section 9.1.4.1.2 of the protocol.

For each treatment period (lead-in, Period I and Period II), the infusion set failure rate (events/patient/30 days) will be calculated for each patient as the total number of events while the patient is on pump and on study treatment divided by the days of exposure [last dose date and time – first dose date and time – duration of pump or treatment interruption] times 30.

The analyses of the primary objective will be conducted on the Safety Population including data collected prior to permanent discontinuation of investigational product (i.e., last dose) in each randomized treatment period (Period I and Period II) and excluding data (if any) that are collected while patients temporarily are off pump or off IP. Treatment group comparisons will be performed using Wilcoxon signed-rank test at the full significance level of 0.05, with patients who are dosed in both treatment periods.

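### SAP Table ITSI.6.3 excludes the data of patients who revoke consent, without date limit or safety exemption; read literally, this conflicts with the Safety Population and data-inclusion rules

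*SAP*

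**What the plan says.** SAP 6.9 introduces Table ITSI.6.3 as a list of important protocol deviations with the way each is identified. In the Revoke Consent row, the identification cell first names the deviation and then adds: "If patient revokes consent, data are excluded from the study". No other row of the table orders data to be excluded, including the rows for consent never obtained and for suspected misconduct.

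The analysis sections contain no matching exception:

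- SAP 6.1 and Protocol 10.2 define the Safety Population as "All randomized patients who receive at least 1 dose of the randomly assigned IP".
- SAP 6.1 says that adverse event analyses "will include all data collected during the course of the entire 6-week treatment period for each treatment group regardless of IP use".
- SAP 6.11.1 runs the primary analysis on the Safety Population, "including data collected prior to permanent discontinuation of investigational product (i.e., last dose) in each randomized treatment period".
- SAP 6.11.1 makes the primary comparison with the "Wilcoxon signed-rank test at the full significance level of 0.05, with patients who are dosed in both treatment periods".

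Protocol 8.2 lists among the grounds for discontinuation that "the patient requests to be withdrawn from the study" and attaches no removal of data to it. SAP 6.3, on dropouts and missing data, does not mention revoked consent. Neither document defines revocation or separates it from withdrawal at the patient's request.

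**The concern.** The study was set up to assess safety comparability, and its primary endpoint is a harm. Revocation happens after dosing and could be prompted by repeated set failures or an adverse event. A rule that drops a patient's data because of such an event can remove the worst experiences from the tables.

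If revocation is linked to harm equally on both insulins, both reported rates come out too low. If the link is stronger on one insulin, the comparison itself is biased, in either direction.

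There is also a practical problem. A programmer working from Table ITSI.6.3 and one working from SAP 6.1 and 6.11.1 could build different analysis datasets from the same SAP.

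**Working it through.** **1. The texts side by side**

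| Rule | Place | Effect on a dosed patient who later revokes |
|---|---|---|
| Data excluded on revocation | SAP Table ITSI.6.3 | Literally, the data go, with no cut-off date |
| Safety Population | SAP 6.1, Protocol 10.2 | Patient stays in |
| Adverse event data | SAP 6.1 | Data collected in the period stay in |
| Primary endpoint data | SAP 6.11.1 | Data to last dose stay in |

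The first row cannot be met together with the other three, and nothing in either document reconciles them. Since little or nothing is collected after revocation, the exclusion would act mainly on data already collected.

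**2. The planning figure**

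SAP 5.2 and Protocol 10.1 give about 42 completers and 12% dropout. 42 / (1 − 0.12) = 47.73, rounded up to 48, which reproduces the plan. Planned dropouts are 48 − 42 = 6 (or 0.12 × 48 = 5.8).

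**3. How many patients**

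No revocation rate is given. Let k be the number who revoke after at least one dose, and assume k = 0 to 6; the upper end treats every planned dropout as a revocation. If all 48 are dosed, the Safety Population is 48 with data kept and 48 − k under the literal rule, so 42 to 48.

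**4. Which analyses change**

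- Revokes in Period I and never starts Period II: already outside the Wilcoxon test. Only rate summaries, adverse event tables and listings change.
- Revokes after dosing in both periods: the Wilcoxon test changes too, and the patient's data on both insulins are lost.

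**5. Possible size (illustration only)**

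Assumptions: 48 patients with full 42-day exposure on each insulin; the same base failure rate b on both insulins; k patients who revoke after dosing in both periods and whose LY900014 failure rate is m times b. The current text gives no event rate, so m = 1, 2 and 4.55 and b = 0.44 events/patient/30 days are range values. The 4.55 and 0.44 appear only in superseded sample-size text in the amendment summary and are not plan inputs.

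LY900014/lispro rate ratio with data kept = [(48 − k) + k × m] / 48. With the data excluded it is 1.00.

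| k | m = 1 | m = 2 | m = 4.55 |
|---|---|---|---|
| 1 | 1.00 | 49/48 = 1.02 | 51.55/48 = 1.07 |
| 3 | 1.00 | 51/48 = 1.06 | 58.65/48 = 1.22 |
| 6 | 1.00 | 54/48 = 1.13 | 69.3/48 = 1.44 |

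The ratio does not depend on b. LY900014 failures removed = k × b × m × 42/30. For k = 3 and b = 0.44 this is 1.8 of 29.6 at m = 1 and 8.4 of 36.1 at m = 4.55.

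For incidence, suppose 8 of 48 patients had an event and 3 of those 8 revoke: 8/48 = 16.7% becomes 5/45 = 11.1%.

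The m = 1 column matters as much as the others. If those who revoke have the same failure rates as everyone else, patients and events are lost but the ratio is not distorted.

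**The case against.** The strongest reply is about location. The sentence stands in a cell meant for identifying deviations, and no analysis section repeats or cites it. The sections that govern the analysis sets keep these patients, and a programmer following them would too. The sentence may be unintended. This stands as far as it goes: the documents show a conflict between a table cell and the governing sections, not that data will be removed. It does not make the sentence harmless, because the cell had already identified the deviation and the added words are an instruction on data.

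Three stronger readings are tempting, and the documents do not support them.

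- *Patients who revoke would also vanish from the disposition counts.* SAP 6.6 counts all randomized patients who complete or discontinue, and SAP 6.9 summarizes and lists important deviations, which include this one, for all randomized patients. If anything, this weighs against reading the cell as wholesale deletion.
- *Every withdrawal triggers the rule.* Protocol 8.2 treats a patient's request to withdraw as a discontinuation with no data consequence. The consent pages are not in the reviewed copy, so what patients were told about data already collected cannot be seen.
- *Protocol 8.2 contradicts the sentence by requiring follow-up.* It says "Patients discontinuing from the study prematurely for any reason should complete AE and other safety follow-up", but this concerns follow-up visits, not which data are analyzed after consent is revoked.

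It is also fair to object that the effect on the primary test is narrow and that bias between insulins needs a link between revocation and outcome. Both points are accepted.

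**Conclusion.** The conflict is real on the plain wording. If the sentence were applied, harm data already collected on study insulin would be dropped because of an event that follows dosing. Reported harms could be understated on either insulin, and the comparison would be biased only if revocation is related to failures or adverse events.

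The size is unknown and may be zero. With one patient who revokes, the illustrated ratio moves by at most 0.07. With three it moves by 0.06 to 0.22, but only under the assumed excess rates of 2 to 4.55. A reader might infer that the safety results are certain to be biased in favor of LY900014. The documents do not support that: they give no revocation rate, no link to outcome and no direction. The point is a low-cost wording correction to make before unblinding, not a defect that undermines the primary analysis.

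**What to change.** Replace the sentence in the Revoke Consent row of Table ITSI.6.3 with:

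> Data collected up to the date of revocation are retained in the Randomized, Safety and CGM Population analyses, unless law or the consent form requires deletion; any such deletions are listed by sequence, period and treatment.

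Add a line, best placed in SAP 6.3, stating that withdrawal at the patient's request under Protocol 8.2 does not trigger exclusion.

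The cost is two sentences in the SAP before unblinding. No change is needed to the design, the populations or the primary test. The one complication is a legal or consent-form duty to delete, which the exception and the listing cover.
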